Only commercially available metallic drug-eluting stents may be used in this protocol. Because the use of DES on patients with left main disease or with three-vessel disease, both of which are off-label uses for DES, is considered investigational, this trial will be conducted under an Investigational Device Exemption (IDE). PCI should be performed using standard techniques at the discretion of the operator. In general PCI should be performed of lesions in vessels with visually estimated reference vessel diameter ≥ 2.25 mm with evidence of a) plaque rupture or thrombosis, or b) with an angiographic diameter stenosis $\geq 80\%$, or c) with evidence of ischemia on either non-invasive testing or by fractional flow reserve ≤ 0.80 or iFR ≤ 0.90 . Which of these criteria are met will be categorized. The specific adjunctive devices used (e.g. atherectomy, cutting/scoring balloons, or aspiration) and techniques (e.g. 1- vs. 2-stent and technique for treatment of bifurcation lesions) will be collected. Bioresorbable vascular scaffolds may not be used in this study.

Procedures may be staged at the discretion of the operator, but the intention to stage procedures must be specified within 24 hours after completion of the first procedure, should ideally be completed within 60 days of the first procedure, and in all cases must be completed within 90 of the first procedure after randomization.

For patients randomized to HCR, if off-pump CAB is performed first, prior to the staged PCI procedure a diagnostic angiogram of the LIMA-LAD graft must be performed, irrespective of the

Optimal Medical Management

All patients should be managed according to guideline-directed medical therapy (GDMT) by clinicians at each clinical site according to generally accepted societal recommendations. Details of GDMT are included in the MOP. Information will be collected about adherence to GDMT.

DEFINITIONS AND MEASUREMENT OF ENDPOINTS

Primary Endpoint

The primary endpoint for this trial is a composite of MACCE over 5 years following randomization.

All MACCE events will be adjudicated by an independent CEC. For the purpose of this trial **MACCE** is defined as a non-weighted composite score comprised of the following components:

- *All-cause mortality*
Death from any cause
- *Stroke*

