Note: Sudden unexpected cardiac death, involving cardiac arrest, often with symptoms suggestive of myocardial ischemia, and accompanied by new ST-segment elevation or new LBBB, and/or evidence of fresh thrombus by coronary angiography and/or autopsy, with death occurring before blood samples obtained, or at a time before the expected appearance of cardiac biomarkers in blood will be classified as a mortality due to peri-procedural MI.

○ *Unplanned Revascularization (adjudicated)*

(a) An unplanned revascularization procedure is defined as any PCI or CABG procedure performed that is an entirely new procedure due to ischemia not included in the pre-specified revascularization strategy, or (b) was included in the pre-specified revascularization strategy as a planned staged procedure, but was performed >90 days after the first revascularization procedure after randomization, or (c) that is a repeat intervention of a previously performed study-related revascularization. Determination as to whether the revascularization procedure involves an original target vessel and lesion or a new (non-target) vessel and lesion will be made by the CEC whenever possible.

Ischemia-driven Unplanned Revascularization

Ischemia-driven *unplanned* revascularization procedures will be assessed. All *unplanned* revascularization procedures will be reviewed and adjudicated by the CEC to determine if they are ischemia-driven. Revascularization will be considered ischemia-driven if the diameter stenosis of the revascularized coronary segment is $\geq 50\%$ or new thrombus and/or ulceration is present, and if any of the following criteria for ischemia are met: i) A positive functional study corresponding to the area served by the target lesion; or ii) Ischemic ECG changes at rest in a distribution consistent with the target vessel; or iii) Typical ischemic symptoms referable to the target lesion; or iv) IVUS of the target lesion with a minimal lumen area (MLA) of $\leq 4 \text{ mm}^2$ for non-left main lesions or $\leq 6 \text{ mm}^2$ for left main lesions; or v) FFR of the target lesion ≤ 0.80 or iFR of the target lesion < 0.90 . A target lesion revascularization for a diameter stenosis less than 50% might also be considered ischemia-driven by the CEC if there was a markedly positive functional study or ECG changes corresponding to the area served by the target lesion.

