Planned staged procedures which are declared within 24 hours of the first revascularization procedure or post randomization and are performed within 90 days of the first post-randomization revascularization procedure will not be considered an unplanned revascularization. Staged procedures performed >90 days after the first post-randomization revascularization procedure, even if originally pre-specified, will be considered an endpoint unplanned revascularization. Intervention on the LIMA, LIMA-LAD distal anastomosis or LAD triggered by routine LIMA angiography prior to a planned staged PCI will not be considered an unplanned revascularization. However, if anterior ischemia occurs after CABG necessitating LIMA angiography prior to the planned staged PCI with subsequent intervention on the LIMA, LIMA- LAD distal anastomosis or LAD, this event will be adjudicated as an unplanned revascularization.

Secondary Endpoints

The secondary endpoints for the trial (each measured at 30 days post procedure, 12, 24, 36, 48, and 60 months, unless otherwise specified) of the trial include:

Cardiovascular Events (adjudicated)

- *MACCE* (defined above) at 30 days post procedure, and 12, 24, 36, 48 months
- *Individual components of MACCE (adjudicated, as defined above):*
 - All-cause mortality
 - Stroke
 - Myocardial infarction
 - Unplanned revascularization
- Ischemia-driven revascularization (*adjudicated*)
- *Cardiovascular and Non-cardiovascular Mortality (adjudicated)*
Cardiovascular mortality, as adjudicated by the CEC, will be assessed. Cardiovascular death includes sudden cardiac death, death due to acute MI, heart failure or cardiogenic shock, stroke, other cardiovascular causes, or bleeding. Non- cardiovascular death is defined as any death with known cause not of cardiovascular causes. Any deaths in which the cause is unknown or undetermined will be considered cardiovascular.
- *Stent thrombosis (adjudicated)*
Stent thrombosis will be adjudicated according to the Academic Research Consortium scale.²⁵ Stent thrombosis will be considered to be present if criteria for definite or probable stent thrombosis are met. According to its timing, stent thrombosis will be further classified as acute (<24 hours), subacute (24 hours – 30 days), early (≤ 30 days), late (> 30 days – 1 year), or very late (> 1 year).
- *Symptomatic graft stenosis or occlusion (adjudicated)*

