Randomization

Must be completed

- (a) within 90 days of the 3-vessel qualifying angiogram for patients identified in the setting of a diagnostic angiogram, or*
- (b) within 90 days following the qualifying 3-vessel angiogram for patients also undergoing a PCI of a non-LAD and non-LM vessel prior to randomization. (See table under Randomization Section)*

The first study intervention is recommended to be performed within 72 hours post randomization and must be performed within 14 days following randomization.

Randomization to the treatment assignment will be generated by the EDC system once the checklist of inclusion and exclusion criteria has been completed and verified and the planned revascularization strategy form has been completed. For the purpose of the primary analysis, patients are considered enrolled in the study once they are randomized and an identification code is generated.

Revascularization Plan

Prior to randomization

The surgical and percutaneous revascularization plan will be described for both HCR and PCI-only revascularization *prior to randomization*. This plan may be revised within 24 hours of the first procedure after randomization to reflect procedural complications, should they occur. Any revascularization procedures deviating from the final revascularization plan in place 24 hours after the first procedure will be considered unplanned revascularization procedures.

Note: Any revascularization procedure that is done during a planned revascularization procedure will NOT be considered an unplanned procedure. E.g.: planned minimally invasive LIMA-LAD procedure becomes complicated by inferior ischemia requiring conversion to an open procedure and RCA bypass; or planned PCI after minimally invasive

LIMA-LAD procedure demonstrated LIMA-LAD graft occlusion requiring PCI; or planned PCI of the LCX results in a LM dissection requiring a LM stent. However, CABG complications that result in separate **unplanned** PCI or CABG procedures, and PCI complications that result in separate **unplanned** PCI or CABG procedures, will be considered unplanned procedures and endpoint events.

Angina Class - Canadian Cardiovascular Society Classification (CCSC)

Following determination of eligibility and within 14 days prior to randomization

The presence of angina will be assessed, and when present, classified according to the CCSC scale and documented on this form. CCSC classification scheme is detailed in Appendix I.

NYHA Class

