Information regarding MACCE, other cardiovascular and bleeding events will be recorded. Limited source documentation pertaining to the MACCE event will be collected and uploaded into the EDC as detailed in the trial Manual of Procedures (MOP).

Long-term Patient-Reported MACCE & QoL***MACCE and Other Cardiovascular and Bleeding Events***

Follow-up must be performed at 6 (± 1), 12 (± 1), 18 (± 1), 24 (± 1), 30 (± 1), 36 (± 1), 42(± 1), 48 (± 1), 54 (± 1), and 60 (± 1) months post-randomization, via centralized DCC telephone follow-up (when allowed by local IRB/REBs)

Follow-up MACCE and other cardiovascular and bleeding event assessments will be conducted via telephone contact with patients by the DCC research nurse. Site coordinators will conduct follow-up via telephone at sites where the IRB/REB does not approve of centralized DCC follow-up. Vital status and the occurrence of any MACCE and other cardiovascular and bleeding event events since the last follow-up will be ascertained.

Information regarding MACCE and other cardiovascular and bleeding event events will be recorded by the DCC research nurse or local site coordinator. In addition, limited source documentation pertaining to the MACCE and selected other cardiovascular events will be collected by the site coordinator and uploaded into the EDC for review by the Clinical Events Committee.

For patients who have completed their planned revascularization procedure(s) as documented on the Planned Revascularization form, including planned staged procedures, any subsequent PCI or CABG performed will be considered an unplanned revascularization, and treated as a MACCE event. As noted in the Definition and Measurement of Endpoints section, this excludes an additional planned staged revascularization if it is declared by the end of the prior planned study intervention procedure.

Medications

At 6 (± 1), 12 (± 1), 18 (± 1), 24 (± 1), 30 (± 1), 36 (± 1), 42(± 1), 48 (± 1), 54 (± 1), and 60 (± 1) months post-randomization, via centralized DCC telephone follow-up (when allowed by local IRB/REBs)

Patient reported medication use since the last follow-up, specifically, antiplatelet and anticoagulant agents, beta blocker, ACE inhibitors, ARB, aldosterone antagonists and statin use will be recorded by the DCC research nurse or local site coordinator.

Angina Class - Canadian Cardiovascular Society Classification (CCSC)

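### The follow-up section exempts late-declared staged procedures that the endpoint definition and the revascularization plan rule do not exempt from primary MACCE

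*Combined protocol and SAP*

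**What the plan says.** Endpoints, Primary Endpoint, makes unplanned revascularization the fourth component of MACCE. Four sections of the protocol then say when a further procedure counts as planned.

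- **Treatment Interventions, Percutaneous Interventions (HCR Group & PCI-only Group):** "the intention to stage procedures must be specified within 24 hours after completion of the first procedure". All stages must be finished within 90 days of that procedure.
- **Definitions and Measurement of Endpoints, under unplanned revascularization:** the exemption covers "Planned staged procedures which are declared within 24 hours of the first revascularization procedure or post randomization", provided they are done within 90 days. A stage done later is an endpoint event even if it was listed in advance.
- **Data Collection, Revascularization Plan:** "Any revascularization procedures deviating from the final revascularization plan in place 24 hours after the first procedure will be considered unplanned revascularization procedures".
- **Data Collection, Long-term Patient-Reported MACCE & QoL:** once the procedures on the plan form are complete, any later PCI or CABG is a MACCE event, with one exception credited to the endpoint definitions: "this excludes an additional planned staged revascularization if it is declared by the end of the prior planned study intervention procedure".

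**The concern.** The first three rules run from the first post-randomization procedure and close after 24 hours. The fourth runs to the end of whichever planned procedure came before the added stage, which may be a second or later one. It presents itself as a restatement of the endpoint definitions, but they do not say this.

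What is at stake is whether a procedure is a primary-endpoint event. The follow-up section is the text used by the data coordinating center nurse or the site coordinator when recording events and assembling source documents for the Clinical Events Committee (CEC). If they apply it as written, a late-declared stage is not treated as MACCE and may not be put forward for adjudication.

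**Working it through.** No plan figure needs to be reproduced. The check sets the rules side by side and runs cases through them.

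| Section | Declaration closes | Clock runs from |
|---|---|---|
| Percutaneous Interventions | 24 hours | completion of the first procedure |
| Endpoint definitions | 24 hours | the first procedure |
| Revascularization Plan | plan as it stands at 24 hours | the first procedure |
| Long-term follow-up | end of the prior planned procedure | no fixed start |

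**Case 1: declared late, done in time.** The plan lists two stages, on days 0 and 30. A third, separate stage is first declared at the end of the day-30 procedure and done on day 60.
- The 24-hour deadline fell on day 1, so the declaration is 30 − 1 = 29 days late. The 90-day limit is met (60 ≤ 90).
- Endpoint definitions: the exemption does not apply.
- Revascularization Plan: the procedure departs from the plan in place at 24 hours, so it is unplanned and a MACCE event.
- Follow-up section: declared by the end of the prior planned procedure, so it is exempt.

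The rules disagree.

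**Case 2: declared early.** A stage is declared 12 hours after the first procedure ends and done on day 40. It meets both the 24-hour and the 90-day limits. With the stage on the plan, the planned procedures are not yet complete, so the follow-up sentence is not triggered. It is planned throughout.

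**Case 3: done after day 90.** The endpoint definitions count it as an event whenever it was declared.

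The conflict is therefore confined to an added stage, in its own session, first declared more than 24 hours after the first procedure and done by day 90.

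**Scale only, on assumed rates.** The documents give no rate for such stages. Let c be the proportion of patients with one, independent of other events, with n = 2354 / 2 = 1177 per arm and the planning rates of 25% (PCI) and 0.80 × 25% = 20% (HCR) when none is counted. Counting them gives HCR = 0.20 + 0.80c and PCI = 0.25 + 0.75c, and extra first events = 1177 × 1.55 × c.

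| c, both arms | Extra first events | Share of 530 | Risk ratio |
|---|---|---|---|
| 0.1% | 1.8 | 0.3% | 0.801 |
| 0.5% | 9.1 | 1.7% | 0.804 |
| 1% | 18.2 | 3.4% | 0.808 |
| 2% | 36.5 | 6.9% | 0.815 |

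If 1% occurred in HCR only, the ratio would be 0.208 / 0.25 = 0.832. If in PCI only, it would be 0.20 / 0.2575 = 0.777. The direction depends wholly on a split between arms that the documents do not give.

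**The case against.** The best reply is that the documents already show which text governs. The follow-up section concerns data collection and defers to the endpoint definitions, three sections agree on 24 hours, and the CEC is charged with applying the pre-specified definitions. On that view this is one badly paraphrased cross-reference. Most of this stands: the definitions are probably meant to prevail. But nothing says so, and the people who apply the follow-up text act before the CEC does.

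A reader might also infer more than the documents support.

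- **That the conflict runs the other way too,** with a stage declared hours after the first procedure being too late under the follow-up rule. That rule starts only once the procedures on the plan form are complete, and the plan can still change in the first 24 hours. Case 2 shows no real conflict.
- **That a revised plan creates a second contradiction.** The Revascularization Plan section says "This plan may be revised within 24 hours of the first procedure after randomization to reflect procedural complications, should they occur", while the definitions count a procedure "that is a repeat intervention of a previously performed study-related revascularization" and also provide that "if anterior ischemia occurs after CABG necessitating LIMA angiography prior to the planned staged PCI with subsequent intervention on the LIMA" or on the LAD, "this event will be adjudicated as an unplanned revascularization". The anterior-ischemia sentence is a specific exception to a general exemption and gives one answer. The Note under Revascularization Plan and the opening of Treatment Interventions point the same way. Making the repeat-intervention limb override every revised plan would be a debatable choice, and it would undercut the reason for allowing revision.
- **That the deadlines differ by up to 90 − 1 = 89 days in practice.** This is arithmetically possible but has little reach, because a stage declared near day 90 must also be done by day 90 to escape being an event.
- **That the result is biased toward one arm.** HCR is described as staged by design and PCI as optionally staged, so exposure to the rule may differ. The rule is worded alike for both arms, and no direction follows.

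**Conclusion.** The follow-up section is wrong as written: it states a deadline for a primary-endpoint exemption that the section it cites does not contain and that three sections contradict. The consequence is limited to Case 1, and it assumes that follow-up staff apply the text they are given. How often such stages occur is unknown, so the effect on the event count and the hazard ratio is unknown in size and direction. The scale figures rest on assumed rates and are not evidence of bias. This is an inconsistency worth correcting because it touches the primary endpoint and costs almost nothing to remove, not because a material effect has been shown.

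**What to change.** 1. In Long-term Patient-Reported MACCE & QoL, delete the separate deadline and refer to the endpoint definitions for which staged procedures are exempt.
2. In Definitions and Measurement of Endpoints, keep a single rule: the stage is declared no later than 24 hours after the first post-randomization procedure is completed, and is done within 90 days of that procedure. Remove the unclear reference to randomization that follows the 24-hour limit.
3. Optional: state there that the pre-specified strategy means the plan as it stands at 24 hours, and that the anterior-ischemia sentence is a specific override.

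The cost is wording in two sections, with no change to sample size, visits or the plan-revision clause. The downside is that a stage first declared at a second stage will count as an event even if it was clinically reasonable, so sites should be told to declare all foreseeable stages within the first 24 hours.
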